8.2. Serious Adverse Events (SAEs)

An adverse event will be classified as serious if it meets any of the following criteria:

- Results in, leads to, or contributes to, a death
- Is life-threatening
- Results in permanent disability or incapacity (i.e., permanent impairment of a body function or permanent damage to a body structure)
- Requires in-patient hospitalization or prolongs hospitalization
- Necessitates medical or surgical intervention to preclude a permanent disability or incapacity
- Results in fetal distress, fetal death or a congenital anomaly/birth defect.

All heart graft-related SAEs will be followed until their resolution.

8.3. Anticipated and Unanticipated Adverse Events

The investigator will assess each adverse event for whether it is anticipated or unanticipated. An unanticipated adverse event is defined as any adverse effect on health or safety, or any life-threatening problem or death caused by, or associated with, a device if that effect, problem or

death was not previously identified in nature, severity or degree of incidence in the investigational plan or application (including a supplementary plan or application), or any other unanticipated serious problem associated with a device that relates to the safety, or welfare of subjects.

Adverse events are associated with heart transplant procedures and have been documented within the first 30 days after heart transplant and are, therefore, anticipated. The list of events includes, but is not limited to:

- Acute rejection
- Atrial and ventricular arrhythmias
- Bleeding (major)
- Hemodynamic instability
- Death
- Fever
- Primary Graft Dysfunction
- Respiratory failure
- Graft failure
- Sepsis
- Renal dysfunction
- Hyperammonaemia
- Malignancy (post-transplant lymphoproliferative disorder (PTLD)
- Multiple organ failure
- Myocardial infarction
- Neurological dysfunction
- Hepatic dysfunction
- Diabetes due to steroid and anti-rejection medications
- Gall stones
- Pancreatitis
- Peptic ulceration
- Gastritis
- Gastro esophageal reflux disease (GERD)
- Aspiration
- Cardiac tamponade
- Pneumo-mediastinum
- Pneumothorax
- Hemothorax
- Pleural bleeding
- Pleural effusion
- Venous thromboembolism (deep venous thrombosis [DVT])
- Pulmonary embolism (PE)
- Sternal wound dehiscence
- Organ deemed not transplantable after retrieval
- Stroke
- Psychosis
- Cerebrovascular accident
- Peripheral vascular clotting or occlusion due insertion of mechanical support

- Limb gangrene due to vascular occlusion due insertion of mechanical support
- Use of mechanical circulatory support
- Coagulopathy
- Hyperacute rejection
- Anastomic site complications; narrowing, bleeding or occlusion
- Delayed sternal wound closure due to compromised cardiac function or excessive bleeding or both
- Bowel thromboembolic complications and gangrene
- Protamine and other anti-heparin medication reaction
- Heparin induced thrombocytopenia

8.4. Unanticipated Adverse Device Effect (UADE)

An UADE means any serious adverse effect on health or safety or any life-threatening problem or death caused by, or associated with, a device, if that effect, problem, or death was not previously identified or encountered before at least once in standard clinical practice, in nature, severity, or degree of incidence in the investigational plan or application (including a supplementary plan or application), or any other unanticipated serious problem associated with a device that relates to the rights, safety, or welfare of subjects.

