8.5. Recording and Reporting of Adverse Event

All heart graft-related adverse events and serious adverse events are to be recorded on the electronic case report forms until post-transplant day 30. The description of the adverse event will include: the date of onset, duration, severity, seriousness, the relationship of the event to the trial treatment, anticipated or not, and any treatment required. All serious adverse events occurring during the course of the first 30 days post-transplant will be reported to TransMedics, Inc., as well as documented on the appropriate electronic case report form(s). For all SAEs, the investigator is required to supply any additional data that may be deemed necessary by the Sponsor. Additionally, any serious adverse events (SAE) and unanticipated adverse device effects (UADE) should be reported to TransMedics, Inc., preferably within 48 hours of the time the investigator learns of the event, but in no case later than 5 working days. Heart graft-related AEs will be recorded up to the 30-day follow-up or through hospital discharge if longer than 30 days. For any particular patient, the Independent Medical Monitor if required to protect patient safety may specify a different follow-up period. The Sponsor is responsible for the classification and reporting of heart graft-related adverse events to the appropriate regulatory authorities, and for the on-going safety evaluation of the trial in accordance with ISO 14155 and governing regulatory requirements.

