13.2. Investigator Reports

In accordance with the FDA reporting requirements, the investigators will be required to prepare and submit to the Sponsor the following complete, accurate, and timely reports on this investigation when necessary:

- The investigator will notify the Sponsor of a subject death occurring during the investigation as soon as possible, preferably within 24 hours of learning of the subject's death, but in no event later than 48 hours. The investigator will also notify the Sponsor immediately of a serious adverse event, preferably within 48 hours of learning of the serious adverse event, but in no event later than 5 working days.
- The investigator will notify the Sponsor of any unanticipated adverse device effects (UADE) preferably within 48 hours after the investigator first learns of the effect, but in no event later than 5 working days. The investigator will notify its IRB or EC of any unanticipated adverse device effects as soon as possible, but no later than 10 working days after the investigator first learns of the effect.
- The investigator will notify the Sponsor of the withdrawal of IRB or EC approval as soon as possible, but no later than 5 working days after the investigator first learns of the withdrawal
- The investigator will provide current progress reports to the Sponsor and reviewing IRB or EC at regular intervals but at least on an annual basis.
- The investigator will notify the Sponsor and the IRB or EC of any deviation from the investigational plan to protect the life and physical well-being of a subject in an emergency as soon as possible, but no later than 5 working days after the emergency occurred.
- The investigator will notify the Sponsor and IRB or EC that an informed consent was not obtained from a subject as soon as possible, but no later than 5 working days after such an occurrence.
- The investigator will provide a final summary report within 3 months after termination or completion of the trial to the IRB or EC. The site trial completion report may serve as the trial completion for the Sponsor
- The investigator will provide any other information upon the request of the IRB or EC, or the Sponsor.

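### Section 8.4 lets a single earlier occurrence in ordinary practice take a serious device effect out of the first limb of the UADE definition, a test that Section 8.3 does not use

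*Protocol*

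**What the plan says.** Protocol Section 8.3 asks the investigator to judge whether each adverse event is anticipated. An effect is unanticipated if it was "not previously identified in nature, severity or degree of incidence in the investigational plan or application". The section then says that certain events "have been documented within the first 30 days after heart transplant and are, therefore, anticipated". It names 47 of them (my count), including death, primary graft dysfunction, graft failure and use of mechanical circulatory support, and leaves the list open: "The list of events includes, but is not limited to".

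Section 8.4 defines a UADE in two limbs. The first covers serious device-associated effects, with nearly the same sentence as 8.3 but with the added condition "not previously identified or encountered before at least once in standard clinical practice". The second covers "any other unanticipated serious problem associated with a device that relates to the rights, safety, or welfare of subjects" and does not carry that condition.

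Two reporting duties use the term. Under Section 8.5, "any serious adverse events (SAE) and unanticipated adverse device effects (UADE) should be reported to TransMedics, Inc., preferably within 48 hours" of the investigator learning of the event, and at the latest within 5 working days. Under Section 13.2, "The investigator will notify its IRB or EC of any unanticipated adverse device effects as soon as possible", and no later than 10 working days after learning of it.

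**The concern.** The two definitions are built on the same sentence but use different yardsticks. Section 8.3 compares the event with what the plan or application identified. Section 8.4 also lets experience outside the trial settle the matter, at the lowest possible threshold of one occurrence. It does not confine that experience to heart transplantation or to any period.

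This matters more here than in a controlled trial. Section 3.1 says that a concurrent control is not possible. Section 10.1 accepts that the hearts used may raise the chance of a graft that functions poorly. Harm from the device could therefore look like a familiar transplant complication that is worse or more common than expected. The severity and incidence wording is what would let such an event count as unanticipated. If one earlier occurrence overrides that wording, the IRB or EC may not get its expedited notice.

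**Working it through.** The plan gives no figure to reproduce, and no arithmetic applies. The check sets the two definitions side by side and then traces what depends on UADE status.

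**Step 1. How the 8.4 sentence can be read.** After the inserted words, the phrase on nature, severity and degree of incidence is detached from its verb.
- *Reading A:* the phrase qualifies both *identified* and *encountered*. An earlier occurrence then excludes an effect only if it was comparable in kind, severity and frequency.
- *Reading B:* the insertion stands alone. One earlier occurrence excludes the effect, whatever its severity or frequency now.

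The text does not decide between them. Under either reading the comparison is no longer with the plan alone.

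**Step 2. Three kinds of serious device-associated effect.**

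| Effect | Definition in 8.3 | First limb of 8.4 |
|---|---|---|
| Not in the plan, never seen in practice | Unanticipated | Qualifies |
| Not in the plan, seen once in practice in a similar form | Unanticipated by the definition, unless the open-ended list is taken to cover it | Excluded under A and B |
| On the 8.3 list, but more severe or more frequent than identified | Unanticipated by the definition, although the list sentence calls the event anticipated without qualification | Can qualify under A, excluded under B |

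The second row is the clear gap. The third row is the ambiguity.

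**Step 3. What depends on UADE status.**

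| Duty or output | Depends on UADE status? | Where |
|---|---|---|
| Investigator to sponsor | No: SAEs and UADEs share the clock of preferably 48 hours, at most 5 working days; deaths preferably 24 hours, at most 48 hours | Protocol 8.5, 13.2 |
| Malfunctions to sponsor | No | Protocol 11.4 |
| Medical Monitor review of SAEs; DSMB review of safety data | No | Protocol 14.9, 14.10 |
| Planned adverse event tables | No: they count unanticipated events, the 8.3 term | Protocol 9.4; SAP 13.1 |
| Investigator to IRB or EC, at most 10 working days | Yes | Protocol 13.2 |

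Section 13.2 gives no matching IRB or EC clock for SAEs in general. Its routine alternative is the progress report, due at least annually.

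**Step 4. Whether the second limb restores what the first loses.** It can, because it has no exemption for earlier occurrence. But it still requires the problem to be unanticipated, and 8.3 treats an open-ended set of post-transplant events as anticipated. An excess of a listed complication is therefore not clearly brought back.

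**The case against.** The strongest reply has four parts.

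1. **The sections define different terms.** Section 8.3 concerns any unanticipated event, and 8.4 a serious device effect, so they need not match. This stands as far as it goes: the fault is an inconsistent shared test, and a reader who infers a direct contradiction goes too far. But nothing in the plan explains why the more serious category should have the more permissive exemption.

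2. **The definition is not emptied.** A reader might infer that almost nothing could be reported as a UADE. The documents do not support that. Effects never met in practice still qualify, the second limb survives, and Reading A keeps the severity and incidence test.

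3. **The sponsor is still told, and other safeguards exist.** A reader might infer that sponsor notification is lost. It is not, because SAEs travel on the same clock. Medical Monitor and DSMB review are also better suited than single-case classification to spotting a raised frequency. This stands, but neither is the expedited IRB or EC notice. The formal stopping rule in 14.10 counts only deaths within 30 days, so it does not stand in for that notice when an effect is non-fatal.

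4. **The 8.3 list already pushes the same way.** Deleting the 8.4 words alone would leave listed events labelled as anticipated. This is correct, and the fix has to address the list as well.

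**Conclusion.** The point holds in a bounded form. Section 8.4 contains an exemption that 8.3 lacks. That exemption can remove a serious device-associated effect from the first limb after one earlier occurrence, and it leaves unclear how a known event at greater severity or frequency is to be classed. The size is not numerical. What can be lost is UADE classification and the 10-working-day IRB or EC notice that follows from it.

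A reader might also suspect that the safety results are distorted. They are not: no endpoint, estimate or planned table uses the UADE definition, and the anticipated-or-not item on the case report form is already governed by 8.3.

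The conclusion rests on the plain wording of 8.3, 8.4, 8.5 and 13.2. It assumes that investigators apply 8.4 as written, and that the second limb is read together with 8.3 on what counts as anticipated. If sites took Reading A and used the second limb generously, the loss would be smaller, but the plan does not tell them to. Because the ambiguity bears on whether an ethics committee is told promptly, at up to 20 sites, it should be corrected.

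**What to change.** - In Section 8.4, cut "not previously identified or encountered before at least once in standard clinical practice" back to its first three words, so that everything from *or* onward goes. The phrase on nature, severity and degree of incidence then attaches directly to *identified*, and 8.3 and 8.4 share one test against the investigational plan or application.
- In Section 8.3, add a sentence saying that an event on the anticipated list is still assessed for nature, severity and degree of incidence, and that listing alone does not settle the matter.

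No change is needed to the case report form or to SAP Table 6.2.

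The cost is one deleted clause, one added sentence and possibly a few more expedited reports to IRBs or ECs. One limit remains: the 8.3 list names events without giving their expected frequencies, so judging a raised incidence of a listed event will still call for clinical judgement.

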8.5. Recording and Reporting of Adverse Event

All heart graft-related adverse events and serious adverse events are to be recorded on the electronic case report forms until post-transplant day 30. The description of the adverse event will include: the date of onset, duration, severity, seriousness, the relationship of the event to the trial treatment, anticipated or not, and any treatment required. All serious adverse events occurring during the course of the first 30 days post-transplant will be reported to TransMedics, Inc., as well as documented on the appropriate electronic case report form(s). For all SAEs, the investigator is required to supply any additional data that may be deemed necessary by the Sponsor. Additionally, any serious adverse events (SAE) and unanticipated adverse device effects (UADE) should be reported to TransMedics, Inc., preferably within 48 hours of the time the investigator learns of the event, but in no case later than 5 working days. Heart graft-related AEs will be recorded up to the 30-day follow-up or through hospital discharge if longer than 30 days. For any particular patient, the Independent Medical Monitor if required to protect patient safety may specify a different follow-up period. The Sponsor is responsible for the classification and reporting of heart graft-related adverse events to the appropriate regulatory authorities, and for the on-going safety evaluation of the trial in accordance with ISO 14155 and governing regulatory requirements.

8.6. Relationship of an Adverse Events to OCS™ Heart

The investigator will assess the relationship of the AE to the OCSTM Heart or to the standard of care, methods of preservation. The relationship will be assessed using the following categories:

- **Definitely Related:** There is a reasonable causal and temporal relationship between preservation with the OCSTM Heart and the adverse event.
- **Probably Related:** It is more likely than not that there is a reasonable causal relationship between preservation with the OCSTM Heart the adverse event.

- **Possibly Related:** There is a reasonable relationship with preservation with the OCSTM Heart and the adverse event, but the causal relationship is unclear or lacking.
- **Unlikely Related:** There is a temporal relationship with preservation with the OCSTM Heart and the adverse event, but there is not a reasonable causal relationship between the trial device and the event.
- **Unrelated:** There is no relationship between preservation with the OCSTM Heart and the adverse event.

8.7. Severity

The investigator will rate the severity of the adverse event using the following categories:

- Mild: The adverse event is transient and/or easily tolerated by the subject.
- **Moderate:** The adverse event causes the subject discomfort and interrupts the subject's usual activities.
- **Severe:** The adverse event causes considerable interference with the subject's usual activities.

8.8. Pre-Existing Conditions

Pre-existing diseases or conditions will not be reported as adverse events.

9. STATISTICAL METHODS

9.1. General

Continuous variables will be summarized using descriptive statistics, specifically the mean, median, standard deviation, minimum, and maximum. Categorical variables will be summarized using frequencies and percentages.

In the case of missing outcome data, a multiple imputation model will be used to present a complete outcome analysis.

9.2. Analysis Populations

9.2.1. Transplanted Recipient Population

The transplanted recipient population will consist of all recipients who are transplanted according to the OCSTM Heart protocol and who have no major protocol violations. The analyses of all effectiveness and safety endpoints, except the rate of donor hearts utilization that were successfully transplanted after preservation and assessment on the OCSTM heart device, will be based on the transplanted recipient population.

For this study, major protocol violations include:

- Donor and recipient's Inclusion/Exclusion Criteria Violation
- Failure to follow IFU
- Failure to follow protocol

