- Adverse Events: All heart graft-related serious adverse events and any heart graft-related adverse events will be followed and documented until the investigator designates the event to be either resolved or its effect on the patient's condition stabilized.
- **Medications:** Medications used to treat all serious heart graft-related adverse event (SAE)-related will be recorded in the trial electronic database until the SAE is resolved

These follow-ups will be attempted within \pm 3 days of the designated periods expect for the PGD Surveillance in the first 24 hours which must be collected at the designated times. The evaluations may be conducted over several days.

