9.3. Analysis of Effectiveness Endpoints

9.3.1. Primary Effectiveness Endpoint

The primary hypothesis for this trial is that the true proportion of transplanted recipients with the composite of patient survival at Day 30 post-transplantation and absence of severe primary heart graft dysfunction (PGD) (left or right ventricle) in the first 24 hours post-transplantation is greater than the Performance Goal value of 0.65. The primary statistical hypotheses are as follows:

 H_0 : $\pi \le 0.65$ and H_1 : $\pi > 0.65$

where π is the true proportion of transplanted recipients with patient survival at Day 30 and absence of severe primary heart graft dysfunction (PGD) (left or right ventricle) in the first 24 hours post-transplant.

The primary effectiveness endpoint will be summarized using counts and percentages and an exact 95% confidence interval for the true percentage based on the binomial distribution. A one-sided exact binomial test at the 0.05 significance level will be performed to test the null hypothesis H₀. This endpoint will be analyzed using the transplanted recipient population.

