9.4. Analysis of Safety

Safety will be analyzed principally by examination of the frequency of adverse events. In particular, the number of donor heart graft-related serious adverse events (SAEs) up to the 30-day follow-up after transplantation per subject will be analyzed. This endpoint is defined to consist of the following adverse events (at most one per type), if they are serious adverse events:

- Primary heart graft dysfunction (not including rejection or cardiac tamponade):
 - Use of ECMO, RVAD, LVAD, BiVAD or insertion of a new IABP for >12 hours post TX.
 - Use of ≥ 2 inotropic agents/vasopressors including high-dose epinephrine or norepinephrine for >7 days post heart TX.
 - Open chest post heart TX. due to compromised heart function
- Primary graft failure requiring re-transplantation

This endpoint will be summarized using descriptive statistics. A 95% confidence interval for the mean based on the t-distribution will be presented.

This endpoint will be analyzed based on the transplanted recipient population.

In addition, the numbers and percentages of subjects experiencing at least one heart graft-related AE, at least one (definitely or probably-related) device-related AE, at least one unanticipated AE, and at least one serious AE, and the number and percentage of deaths will all be tabulated. Also, the number of heart graft-related adverse events and the number and percentage of subjects experiencing adverse events will be tabulated by system organ class and preferred term using MedDRA. A similar analysis will be performed for serious AEs. AEs will also be tabulated at the event level by system organ class and preferred term and the relationship of the adverse event to the device using counts and percentages. Similar analyses will be performed by the severity of the adverse event.

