6.0 ANALYSIS POPULATIONS

The Transplanted Recipient Population will consist of all recipients who are transplanted according to the OCS™ Heart protocol and who have no major protocol violations. The analyses of all effectiveness and safety endpoints, except the rate of donor hearts utilization that were successfully transplanted after preservation and assessment on the OCS™ heart device, will be based on the Transplanted Recipient Population.

For this study, major protocol violations include:

- Donor and recipient's Inclusion/Exclusion Criteria Violation
- Failure to follow IFU
- Failure to follow protocol

The OCS™ Heart Population will consist of all donor hearts that are transported by the OCS™. The analysis of the rate of donor hearts utilization that were successfully transplanted after preservation and assessment on the OCS™ heart device will be based on the OCS™ Heart Population.

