In addition, the numbers and percentages of subjects experiencing at least one serious adverse event (AE), at least one heart graft-related AE, at least one severe heart graft-related AE, at least one device-related heart graft-related AE (AEs that are probably or definitely related to the investigational device or for which the relationship is missing), at least one unanticipated heart graft-related AE, and at least one heart graft-related serious AE, and the number and percentage of deaths will be tabulated (Table 6.2). Also, the number of heart graft-related AEs and the number and percentage of subjects experiencing heart graft-related AEs will be tabulated by system organ class (SOC) and preferred term (PT) using MedDRA (Table 6.3). Similarly, the number of SAEs and the number and percentage of subjects experiencing SAEs will be tabulated by system organ class (SOC) and preferred term (PT) using MedDRA (Table 6.4), and the number of heart graft-related serious AEs and the number and percentage of subjects experiencing heart graft-related serious AEs will be tabulated by SOC and PT using MedDRA (Table 6.5). The number and percentage of heart graft-related AEs will be tabulated by SOC and PT and the relationship of the adverse event to the device (related versus not related, where AEs with a probable or definite relationship to the investigational device are classified as related, and AEs with a possible, unlikely, or unrelated relationship are classified as not related) (Table 6.6) and by SOC and PT and severity (Table 6.8). The number and percentage of subjects experiencing heart graft-related AEs will be tabulated by SOC and PT and the relationship of the adverse event to the device (related versus not related) (Table 6.7) and by SOC and PT and severity (Table 6.9).

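### The primary test, safety endpoint and planned death tables all use one per-protocol recipient set; no all-transplanted analysis is planned, and nothing fixes 'major' violations before lock or blind to outcome

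*Protocol*

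**What the plan says.** The set called the Transplanted Recipient Population is a per-protocol set. Protocol 9.2.1 limits it to "recipients who are transplanted according to the OCSTM Heart protocol and who have no major protocol violations", and SAP 6.0 repeats the definition. Three kinds of major violation are listed: donor or recipient eligibility violations, "Failure to follow IFU" and "Failure to follow protocol".

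This set is used for:

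- the primary test (Protocol 9.3.1): "This endpoint will be analyzed using the transplanted recipient population";
- 30-day survival and severe PGD as secondary endpoints (Protocol 9.3.2, SAP 12.2);
- the safety endpoint (Protocol 9.4): "This endpoint will be analyzed based on the transplanted recipient population";
- Kaplan-Meier survival (Table 4.5 in the SAP list of tables);
- deaths. SAP 13.1 says "the number and percentage of deaths will be tabulated (Table 6.2"), and the list of tables gives Table 6.2 this population. The deaths on study in Table 1.1 (SAP 7.0) are limited to it too.

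SAP 6.0 states the scope generally: "The analyses of all effectiveness and safety endpoints, except the rate of donor hearts utilization". The only other analysis set is of donor hearts. The hypothesis, in Protocol 9.3.1 and SAP 12.1, is about the true proportion among transplanted recipients and mentions no violation filter.

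Protocol 14.8 records deviations on an eCRF, and Protocol 14.9 has the Medical Monitor evaluate them. Neither section sets a time for classification or requires that outcome be unknown. SAP 8.0 tabulates deviations (Table 1.3) only in the retained set.

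**The concern.** There is no control arm. The result is one proportion set against a fixed goal of 0.65, so removing recipients acts directly on the estimate. If violators fail more often than others, the success rate is biased upward and the SAE and death rates downward. If exclusion is unrelated to outcome, that bias does not arise. The planned tables would not show which case holds: Table 1.3 omits the excluded recipients, and the Table 1.1 categories in SAP 7.0 include none for recipients transplanted but excluded.

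Deaths show the problem most clearly. The stopping rule in Protocol 14.10 covers recipients transplanted with an OCS-treated heart, with no violation filter. A recipient who dies by Day 30 and is judged a major violator counts toward stopping, but drops out of the primary result and the deaths in Tables 1.1 and 6.2.

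**Working it through.** **Inputs.** One-sided exact binomial test, alpha 0.05, goal 0.65 (Protocol 9.3.1); true rate 0.80, power 80%, N=55, rejection at 42 of 55 (Protocol 9.6); N raised to 75 (SAP 3.4). The documents give no exclusion rate, so every exclusion rate below is an assumption.

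**The plan's own figure.** With X ~ Bin(55, 0.65), P(X ≥ 42) = 0.0489 and P(X ≥ 41) = 0.0874, so 42 is the correct cut-off. At 0.80, P(X ≥ 42) = 0.803. The stated design reproduces.

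**At 75.** P(X ≥ 56 | 75, 0.65) = 0.0485 and P(X ≥ 55 | 75, 0.65) = 0.0799. The cut-off is therefore 56, and power at 0.80 is 0.900.

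**What a few exclusions do.** Start from 55 successes in 75 transplanted, one short of the cut-off:

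| Dropped | Retained result | p against 0.65 | Test |
|---|---|---|---|
| none | 55/75 | 0.080 | fails |
| 1 failure | 55/74 | 0.057 | fails |
| 2 failures | 55/73 | 0.039 | passes |
| 1 success, 1 failure | 54/73 | 0.067 | fails |
| 1 success, 2 failures | 54/72 | 0.046 | passes |
| 2 successes, 1 failure | 53/72 | 0.077 | fails |

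**Type I error when the true all-transplanted rate is 0.65.** Let eS and eF be the assumed exclusion rates of successes and failures. Put s = 0.65(1 − eS) and f = 0.35(1 − eF). The retained success rate is s/(s+f). For example, at 5%/10%, s = 0.6175, f = 0.315 and s/(s+f) = 0.662.

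SAP 3.4 does not say whether 75 is the count before or after exclusion, so both are shown. Before: the retained number m ~ Bin(75, s+f), successes ~ Bin(m, s/(s+f)), with the exact 0.05 cut-off at each m. After: P(X ≥ 56 | 75, s/(s+f)).

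| eS / eF | 75 before exclusion | 75 after exclusion |
|---|---|---|
| 5% / 5% | 0.038 | 0.049 |
| 10% / 5% | 0.023 | 0.030 |
| 5% / 8% | 0.049 | 0.063 |
| 5% / 10% | 0.058 | 0.075 |
| 5% / 15% | 0.088 | 0.113 |

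Error exceeds 0.05 only when failures are excluded sufficiently more often than successes. Exclusion at 5% regardless of outcome costs power instead: 0.859 against 0.900, with 75 before exclusion.

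**The case against.** Several points against the concern have force.

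- A reader might infer that any departure excludes a recipient, even a mistimed PGD reading, since Protocol 7.2 says of "PGD Surveillance in the first 24 hours which must be collected at the designated times". The documents do not support that. Table 1.3 tabulates deviations among recipients already free of major violations, so a lesser tier must exist, and Protocol 14.8 treats significant deviations separately. Severe PGD-LV, and need for an RVAD, also rest on mechanical support rather than a timed reading (Appendix 1). What stands is that no written threshold separates the tiers.
- The IFU is not among the documents. One can say that the protocol and SAP give no threshold for an IFU failure, not that the IFU itself gives none.
- Eligibility violations can be checked before transplant, and IFU failures in preservation also precede the outcome. The Medical Monitor is independent, and PGD endpoints use adjudicated results (SAP 4.0). This narrows the room for outcome-driven exclusion, but it is not classification blind to outcome or fixed before lock.
- Excluded recipients stay in the listings (SAP 5.1), including the analysis-population listing for consented recipients, so their outcomes could be compared by hand. SAE reporting (Protocol 8.5) and the stopping rule state no violation filter. A reader might infer a gap in safety monitoring; there is none on this ground. The gap is in planned tests and summary tables.
- The hypothesis wording may be shorthand for the defined set. Even so, no analysis covers all transplanted recipients.
- The example starts one success below the cut-off. At a true rate of 0.80, exactly 55/75 has probability 0.039.

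**Conclusion.** The concern holds as a gap in pre-specification and reporting. One per-protocol set carries the confirmatory test, the safety endpoint and the planned death tables. The protocol and SAP leave the line between major and lesser IFU or protocol failures undrawn, and nothing requires it to be drawn before database lock or without knowledge of outcome. Because a Day-30 death can be left out of the primary result and the planned death tables, this is more than missing detail and should be fixed.

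The size is conditional. Near the cut-off, dropping two failures can reverse the conclusion; dropping one does not. With 75 before exclusion and 5% of successes excluded, type I error is still 0.049 when 8% of failures are excluded, and reaches 0.058 at 10% and 0.088 at 15%. If 75 is the count after exclusion, 5%/10% gives 0.075. A reader might infer that the trial's error rate is inflated. The documents do not show that: they give no exclusion rate and no evidence that violators fail more often.

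**What to change.** In Protocol 9.2.1 and SAP 6.0:

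1. Add a set of all recipients transplanted with an OCS-preserved heart, and make it the main set for SAEs and deaths.
2. Report the primary endpoint test in that set as a pre-specified analysis beside the current set, and label the current set per-protocol. Whether the all-transplanted set should be primary for effectiveness is the sponsor's choice.
3. State in writing what makes an IFU or protocol failure major, and have violations classified before database lock by people unaware of outcome.
4. Show transplanted-but-excluded recipients in Table 1.1 with reason and outcome, and run Table 1.3 on all transplanted recipients.

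No new patients or data are needed. The cost is a SAP revision and repeated tables. Changing Protocol 9.2.1 also needs an amendment with IRB/EC approval, and possibly FDA approval (Protocol 16). The headline rate may be less favourable if violators fail more often. Tested on 75 recipients with none excluded, the cut-off is 56, with exact alpha 0.0485 and power 0.900 at 0.80.
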